5.3. Lifestyle Considerations

No lifestyle restrictions are required.

5.4. Screen Failures

Screen failures are defined as participants who consent to participate in the clinical study but are not subsequently entered in the study because they did not meet all inclusion criteria or meet one or more exclusion criteria. A minimal set of screen failure information is required to ensure transparent reporting of screen failure participants to meet the Consolidated Standards of Reporting Trials (CONSORT) publishing requirements and to respond to queries from regulatory authorities. Minimal information includes demography, screen failure details, eligibility criteria, and any SAE.

Individuals who do not meet the criteria for participation in this study (screen failure) may be rescreened once at the Investigator's discretion. If a participant can be rescreened, the PI is to consult with the Medical Monitor to determine whether some or all of the screening assessments must be repeated. Rescreened participants will sign a new ICF and will be assigned a new participant number.

5.5. Criteria for Temporarily Delaying Inpatient Treatment Period

Following successful screening and meeting of study eligibility criteria, the inpatient treatment period and RHC procedure must be scheduled without delay.

The scheduled treatment period may be temporarily delayed no longer than 28 days by the Investigator in consultation with the Medical Monitor for valid reasons. Examples of valid reasons for delaying the treatment period may include such things as a life event for the participant (eg death in the family), local public health emergency (e.g., COVID 19 outbreak), site facility issues (e.g., catheterization lab or ICU bed availability), or pending TPIP dosing directives from the SRC.

A temporary delay in the scheduled inpatient treatment period for a valid reason may result in previously met Inclusion Criteria that rely on a time window to be not met (e.g., 6MWD falls outside the 6 months prior to Baseline window). This is not considered to be a Screen Failure. In this case, the Investigator should consult with the Medical Monitor to identify which screening tests need to be conducted or repeated to ensure that the participant meets study inclusion criteria and can safely participate in the study.

Deterioration of the participant's medical condition is not a valid reason to delay start of the inpatient treatment period. In some cases, delaying the inpatient treatment period may cause the participant to meet one or more exclusion criteria (e.g., participant develops a lower respiratory infection). In this case the participant should be considered a Screen Failure and [Section 5.4](#) applies.

6. STUDY IMP AND CONCOMITANT THERAPY

Study IMP is defined as any investigational intervention(s), marketed product(s), placebo, or medical device(s) intended to be administered to a study participant according to the study protocol.

6.1. Study IMP Administered

6.1.1. Inpatient Treatment Period (Single Dose)

A single dose of TPIP will be used in the inpatient treatment period. Each TPIP capsule contains 7.5 mg of dry powder, containing 112.5 µg of the TP prodrug. A dose may consist of a single capsule or of multiple capsules administered in succession.

Name of Treatment	Dose	Supplied Formulation	Route and Frequency of Administration
Treprostinil palmitil inhalation powder (TPIP)	One or more single actuation capsules	Single actuation capsules containing 112.5 µg TP per 7.5 mg powder	Inhalation; single dose after Baseline assessments
Treprostinil palmitil inhalation powder (TPIP)	One or two single actuation capsules (80 µg, 160 µg, 240 µg, 320 µg, 400 µg, 480 µg, or 640 µg)	Dry powder single actuation capsules containing 80 µg, 160 µg, or 320 µg	Inhalation; single dose after Baseline assessments

QD = once daily

6.1.2. Optional Extended Use Treatment Period

The IMP used in the EUT period will be capsules containing 1 of 3 dosage strengths of TPIP (80 µg, 160 µg, or 320 µg). IMP should be taken around the same time every day. Administration of IMP will be via inhalational dry powder packaged in single actuation capsules. One or 2 capsules will be administered for each dose. Administration of 2 capsules should be done sequentially. Each TPIP capsule contains 8 mg, 16 mg, or 32 mg of dry powder containing 80 µg, 160 µg, or 320 µg of the TP prodrug, respectively.

Name of Treatment	Dose	Supplied Formulation	Route of Administration
Treprostinil palmitil inhalation powder (TPIP)	One or two single actuation capsules (80 µg, 160 µg, 240 µg, 320 µg, 400 µg, 480 µg or 640 µg QD)	Dry powder single actuation capsules containing 80 µg, 160 µg, or 320 µg	Inhalation (QD)

QD = once daily

6.1.3. Medical Devices

In the planned clinical study, the TPIP will be administered by oral inhalation using a Plastiape capsule-based Dry Powder Inhaler (RS 01 Mod 7). A Type III Drug Master File is filed at the US FDA and the RS01 inhaler is classified as a Class I medical device. The Instructions for Use of the device document is provided separately as an Appendix to the Pharmacy Manual.

All device deficiencies (including malfunction, use error, and inadequate labeling) shall be documented and reported by the Investigator throughout the clinical investigation ([Section 8.3.7](#)) and appropriately managed by Insmed.

6.2. Preparation/Handling/Storage/Accountability

Insmed Incorporated will provide the Investigator and clinical unit with adequate quantities of TPIP capsules. For 112.5 µg doses, TPIP-filled HPMC capsules will be delivered in HDPE bottles overwrapped with an aluminum pouch, containing a sachet of desiccant to prevent moisture ingress. For 80 µg, 160 µg, or 320 µg doses, HDPE bottles will be closed with the desiccant placed inside the bottle, and induction sealed. The powder will be administered by oral inhalation using a Plastiape capsule-based Dry Powder Inhaler.

6.2.1. Inpatient Treatment Period (Single-dose)

Directions for preparation and administration of the TPIP dose to the participant are provided in a separate document as an Appendix to the Pharmacy Manual for the single-dose Inpatient Period.

All study IMP must be stored according to the labeled instructions in a secure cabinet or room with access restricted to necessary clinic personnel. The site will be required to keep a temperature log to establish a record of compliance with storage conditions. Current stability data supports the shelf life assigned to TPIP when stored at 2 to 8 °C.

- The Investigator or designee must confirm appropriate temperature conditions have been maintained during transit for all study IMP received and any discrepancies are reported and resolved before use of the study IMP.
- Only participants enrolled in the study may receive TPIP and only authorized site staff may supply or administer it. All TPIP must be stored in a secure, environmentally controlled, and monitored (manual or automated) area in accordance with the labeled storage conditions with access limited to the Investigator and authorized site staff.
- The Investigator, institution, and/or pharmacist or designee is responsible for study IMP and dosing devices accountability, reconciliation, and record maintenance (e.g., receipt, reconciliation, and final disposition records).
- Study IMP and dosing device accountability records will be maintained for all clinical supplies. All transactions will be recorded on the drug and dosing device accountability records including shipment receipts and study participant doses. All transactions will be recorded on a real-time basis.

- The Investigator/site will maintain detailed documentation of the number and identification of bottles and dispensing units of TPIP with copies of these documents to be provided to Insmed at the end of the study. All used and unused study IMP and dosing devices will be maintained by the site until inventoried by the study monitor. Upon completion of the study IMP and dosing device inventory by the study monitor, used and any unused study IMP and dosing devices will be disposed of in accordance with instructions provided to sites and according to site destruction policies. Documentation of destruction must be provided to Insmed.
- Further guidance and information for the final disposition of unused study IMP supplies can be obtained from Insmed.

6.2.2. Optional Extended Use Treatment Period

Directions for preparation and administration of IMP to the participant in-clinic are provided in the Pharmacy Manual for the optional EUT period. Directions for preparation and administration of IMP for home use will be provided to the participants.

Only participants enrolled in the study may receive IMP, and only authorized study personnel may supply IMP. All IMP must be stored according to the labeled instructions with access restricted to necessary clinic personnel. The site will be required to keep a temperature log to establish a record of compliance with storage conditions. Refer to the Pharmacy Manual for the optional EUT period for shelf-life and storage conditions.

The Investigator, institution, or the head of the medical institution (where applicable) is responsible for IMP and dosing devices accountability, reconciliation, and record maintenance (e.g., receipt, reconciliation, and final disposition records). Directions for storage, handling, accountability, and destruction are provided in the Pharmacy Manual for the optional EUT.

6.3. Measures to Minimize Bias: Randomization and Blinding

Not applicable.

6.4. Study Intervention Compliance

6.4.1. Inpatient Treatment Period (Single Dose)

Study participants will receive the TPIP dose directly from the Investigator or designee, under medical supervision, in an appropriate inpatient setting. The date and time of the dose administered will be recorded in the source documents. The dose of TPIP and study participant identification will be confirmed at the time of dosing by a member of the study site staff other than the person administering the TPIP.

6.4.2. Optional Extended Use Treatment Period

At each in-clinic visit, participants will be dispensed adequate IMP to allow for daily dosing. When participants are dosed at the site, IMP administration will be overseen by study site personnel. The date and time of each dose self-administered in the clinic will be recorded in the

source documents. The dose of IMP and study participant identification will be confirmed at the time of dosing by a member of the study site personnel.

When participants administer IMP at home, compliance with IMP will be assessed at each in-clinic visit. Participants will record their daily dose on paper dosing diaries. Compliance will be assessed by direct questioning, review of participant dosing diaries, and counting of returned capsules during the site visits. Participants will return unused capsules and used study capsules and devices to the study site at each in-clinic visit. Participants who undergo a study drug taper will return unused capsules and used capsules and devices to the study site at a follow-up visit. Unused capsules should be returned in the bottle they were dispensed in. Deviation(s) from the prescribed dosage regimen should be recorded.

A record of the quantity of capsules dispensed to and administered by each participant must be maintained and reconciled with study drug logs and participant dosing diaries. Study drug start and stop dates, including dates for study drug interruptions and/or dose reductions will also be recorded.

6.5. Dose Modification

Dose modification is part of the study design and is described in detail in [Section 4.3](#) and [Section 1.3.2](#).

6.6. Continued Access to Study Intervention After the End of the Study

Not applicable.

6.7. Treatment of Overdose

An overdose is defined as the participant receiving any TPIP in excess of their assigned dose as predetermined by the SRC ([Section 4.3](#)). An overdose itself is not an AE. However, if the overdose results in clinical signs and symptoms, it requires expedited reporting as if it is an SAE. The Investigators must refer to the relevant documents for detailed information regarding warnings, precautions, contraindications, AEs, and other significant data pertaining to the study IMP. Such documents may include, but are not limited to, the Investigator's brochure.

In the event of an overdose, the Investigator must:

- Contact the Medical Monitor within 24 hours.
- Evaluate the participant to determine, in consultation with the Medical Monitor, how to proceed with treatment period procedures and assessments.
- Closely monitor the participant for any AE/SAE and laboratory abnormalities until TP or TRE is likely to be sufficiently metabolized and/or excreted and/or can no longer be detected systemically. The frequency and duration of plasma sampling from the last dose of TPIP must be determined by the Investigator in conjunction with the study team and Medical Monitor.
- The overdose must be fully documented (e.g., quantity of the excess dose, duration of the overdose, how it happened) in the CRF.

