1.3.2.2. Optional Extended Use Treatment Period

Entrance into the optional EUT period is at participants' and Investigators' discretion and begins with a titration. The guideline for the optimal 3-week planned titration schedule is provided in [Figure 4](#). The target TPIP dose will be achieved with a combination of dry powder capsules containing 80 µg, 160 µg, and 320 µg of TP.

[figure not shown]
During the titration period (EUT Days 1 to 21), each participant's dose will be up-titrated to the highest tolerated dose for that individual. Participants will start open-label study drug with 1 capsule (80 µg TPIP) QD. If this dose is well tolerated, the dose should be up-titrated until reaching the participant's highest tolerable dose as described by the dosing schedule in [Figure 4](#). During this titration period, participants must stay on study drug for the minimum number of cumulative days required for each dose (e.g., 2 days at 80 µg, 160 µg, or 240 µg; 3 days at 320 µg; or 4 days at 400 µg or 480 µg) prior to titrating to the next higher dose. Study drug titration may occur slower, but not faster, than described in [Figure 4](#). If a dose is not tolerated, study drug may be decreased to the previous dose level. At the Investigator's discretion, up-titration may resume (as described in [Figure 4](#)) until the participant's highest tolerated dose is achieved at EUT Day 21.

All dose adjustments must be preceded by contact with the Investigator or study site personnel. In addition, the Investigator and/or study site personnel will be in contact with participants during the dose adjustment period to assess the tolerability to study drug as measured by the AEs commonly observed with other prostacyclin receptor agonists, which include headache, flushing, nausea, cough, and muscle pain. The decision to up-titrate to the next TPIP dose will be based on safety and tolerance data (e.g., AEs) as reported by the participant and assessed by the Investigator.

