At the Investigator's discretion, based on tolerability, the study drug dose may be increased by 1 dose level (as described in [Figure 4](#)) at the EUT Week 5 in-clinic visit for participants who have not achieved the 640 µg dose. The increase in dose will be administered under clinical observation at the study site to ensure tolerability and correct dosing and self-administration of study drug. The participant's highest dose tolerated is expected to continue for the remainder of the study after the EUT Week 5 visit.

At the Investigator's discretion, participants may undergo a study drug taper for up to 2 weeks after the EUT Week 16 visit to help facilitate a safe withdrawal from study drug. The Investigator and/or study site personnel will be in contact with participants during the study drug taper to assess the tolerability to study drug.

Figure 4: Guideline for Optimal 3-Week Planned Titration Schedule (Optional Extended Use Treatment Period)

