2.3.3. Overall Benefit: Risk Conclusion

Although participants may or may not benefit individually from this study, risks to their well-being will be carefully monitored and managed throughout their participation. Insmed considers the risks to be appropriate to the value of the knowledge gained in this study about the characteristics of this promising therapy. The well-characterized safety profile of TRE and the

continued safety monitoring by both the Investigator and SRC (in the inpatient treatment period, observation period, and optional EUT period, if applicable) will minimize risk to participants. Most TEAEs observed with exposure to this drug are events known to be associated with prostanooids and their agonists. Study inclusion and exclusion criteria will help to ensure that only appropriate participants are enrolled. Risks involved with study procedures and settings will be managed by the relevant Investigator and institutional processes.

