4.3.2. Optional Extended Use Treatment Period

Selection of once-daily inhalation of TPIP at 80 – 640 µg was based on clinical PK and safety data from healthy participants, predicted efficacious dose levels using pre-clinical data, safety margin from rat and dog NOAEL doses, and Tyvaso® clinical experience.

In Phase 1 studies, TRE PK was linear, and the systemic exposure was dose proportional. Single doses of up to 675 µg and multiple doses of up to 225 µg TPIP QD for 7 days were generally well tolerated. Most AEs observed were mild in severity and consistent with the safety profile of other prostanoïd therapies.

Based on exposures following a single dose of TPIP 675 µg in Study INS1009-102, TRE exposures in this study are not anticipated to exceed those following administration of the currently approved treprostinil product, Remodulin®. Treprostinil exposures following a continuous IV infusion of 10 ng/kg/min Remodulin (C_{max} 1,470 pg/mL; AUC 25,690 pg*h/mL) are reported to be 2.1-fold and 4.7-fold higher, respectively, than those observed following administration of TPIP 675 µg (C_{max} 717 pg/mL; AUC 5,480 pg*h/mL) ([Laliberte et al., 2004](#)). Minimal accumulation was observed following repeat doses of TPIP 225 µg QD for 7 days, and since a lower maximum dose (640 µg) will be used in the extended use portion of this study,

TRE exposures are expected to be lower than those observed following single doses of TPIP 675 µg in Study INS1009-102.

Based on the findings above, the TPIP dose will range from 80 µg to 640 µg QD in this treatment period.

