10.1.7. Committee Structure

An SRC will be responsible for monitoring safety data. The SRC will comprise all Investigators and key members of the Insmed Study Team (including but not limited to Medical Monitor, Medical Director(s), Safety/Pharmacovigilance Physician, Statistician, Clinical Pharmacologist) and external expert consultants. The SRC will continuously monitor all available safety, PD and PK data for each participant and will obtain consensus regarding the safety of continuing the study, the next TPIP dose, and clinical care of the next participant. Expert consultants may be invited to review and interpret participant data. With any safety findings, a decision will be made, based on the review, as to whether enrollment in the study will be allowed to continue. Decisions regarding final database values for PD parameters may be adjudicated by the SRC.

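### Section 6.7 measures overdose against an SRC-assigned dose, but no extended-use dose is assigned by the SRC, so as written its overdose actions do not reach extended-use dosing errors

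*Protocol*

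**What the plan says.** Section 6.7 (Treatment of Overdose) is not divided by study period. It opens: "An overdose is defined as the participant receiving any TPIP in excess of their assigned dose as predetermined by the SRC", citing Section 4.3. What follows depends on that sentence. A symptomatic overdose is to be reported on the expedited SAE route. The Investigator must also contact the Medical Monitor within 24 hours, agree with the Medical Monitor how to proceed, monitor closely, and document the overdose fully in the CRF.

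The SRC's dosing task is set out in Sections 1.3.2.1, 4.3.1 and 10.1.7. It chooses each participant's single dose in turn. Section 10.1.7 says that it "will obtain consensus regarding the safety of continuing the study, the next TPIP dose, and clinical care of the next participant".

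EUT dosing is in Section 1.3.2.2. Participants start at 80 µg once daily and are titrated to their individual highest tolerated dose. The decision to step up is "based on safety and tolerance data (e.g., AEs) as reported by the participant and assessed by the Investigator". At Week 5, at the Investigator's discretion and "based on tolerability, the study drug dose may be increased by 1 dose level". A taper of up to 2 weeks is also at the Investigator's discretion.

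For home dosing, Section 6.4.2 relies on paper diaries and capsule counts and says: "Deviation(s) from the prescribed dosage regimen should be recorded".

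**The concern.** The definition names a decision-maker who has no dosing role in the EUT. The protocol began as a single-dose study, where an SRC-assigned dose was the only dose there could be. Amendment 1 added 16 weeks of daily dosing, mostly at home, from three capsule strengths and with the dose changing during titration. Dosing errors are more plausible there than for a supervised inpatient dose, which a second staff member confirms (Section 6.4.1). If the definition does not reach those errors, a site following the text has no stated duty to call the Medical Monitor or to start the Section 6.7 follow-up. Nor must it send an expedited report for a symptomatic but non-serious overdose.

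**Working it through.** No arithmetic decides this, and the plan states no figure to reproduce. The check is whether any text lets the Section 6.7 condition be met for an EUT dose.

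1. **Who assigns the reference dose in the inpatient period?** The SRC, participant by participant (Sections 1.3.2.1 and 4.3.1). The definition works as intended here.

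2. **Who assigns it in the EUT?** The Investigator, on tolerability (Section 1.3.2.2). The choice is bounded. The protocol fixes the starting dose, the minimum days at each level, the levels themselves and the 640 µg maximum. Contact with the site must precede every adjustment. None of these steps passes through the SRC.

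3. **Does the SRC have any other EUT role?** Section 2.3.3 refers to "continued safety monitoring by both the Investigator and SRC (in the inpatient treatment period, observation period, and optional EUT period, if applicable". That is monitoring, not dose assignment, and Section 10.1.7 ties the SRC's dosing decision to the next participant.

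4. **Does the cross-reference to Section 4.3 help?** Section 4.3 now contains Section 4.3.2 on the EUT, which says: "Based on the findings above, the TPIP dose will range from" 80 to 640 µg once daily. It gives a range, assigns no individual dose and does not mention the SRC. On the most generous reading, an EUT overdose would mean more than 640 µg. A participant prescribed 160 µg who takes 320 µg or 480 µg would still not qualify, because both are below 640 µg.

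5. **Is the wording deliberate?** The same definition, with the same pointer to Section 4.3, stands in Section 6.7 of the single-dose protocol (version 1.0). Amendment 1 split Sections 6.1, 6.2, 6.4 and 7.1 to add EUT text. It also updated nearby Section 6.5, which now reads "Dose modification is part of the study design and is described in detail in" Sections 4.3 and 1.3.2, where version 1.0 cited only Section 4.3. Section 6.7 received no matching change. This looks like carried-over wording, not a choice.

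6. **What other text covers an EUT error?**
   - Section 6.4.2: the deviation is recorded, and capsules are counted and reconciled.
   - Section 10.3.1: signs or symptoms of a suspected overdose are AEs, with no SRC condition. An overdose in itself is not reported as an AE or SAE unless it is intentional with possible self-harming intent.
   - Section 8.3.1: any SAE is reported within 24 hours.

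7. **What remains uncovered?** An accidental overdose without symptoms is left as a recorded dosing deviation. A symptomatic, non-serious one is an ordinary AE. In neither case does the text require the 24-hour Medical Monitor contact, the close monitoring or the CRF overdose detail. In the second case it also does not require expedited reporting.

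**The case against.** The best answer is that nobody would read Section 6.7 this way. Its working idea is TPIP above the assigned dose, Section 10.3.1 speaks of suspected overdose without mentioning the SRC, and a site that sees twice the prescribed dose taken would probably call it an overdose. Much is also handled already. Diary review and capsule reconciliation largely capture the quantity, and Section 8 lets the Investigator take extra safety samples and make extra assessments at any time. All of this stands, and it limits the weight of the point. It does not remove it, because mandatory duties and an expedited reporting rule should not depend on sites reading past the stated reference dose.

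A reader might infer three stronger things, which the documents do not support.

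- **That EUT overdoses go unhandled.** They do not, as the recording and AE provisions above show.
- **That the gap is large because daily EUT doses far outnumber the single inpatient dose.** That counts planned doses, not errors. The protocol gives no error rate.
- **That there is a shown exposure hazard.** A double dose at the top level would be 2 × 640 = 1,280 µg, above the 675 µg highest single dose tested. But scaling the 717 pg/mL C_max in Section 4.3.2 in proportion to dose gives 717 × 1,280 / 675 ≈ 1,360 pg/mL, below the 1,470 pg/mL quoted there for the IV comparator. That extrapolates beyond the tested range and has no bearing on whether the definition is right.

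**Conclusion.** The point holds as a minor safety-reporting correction. Section 6.7 names the wrong reference dose for the EUT, and read as written its follow-up and expedited reporting do not apply to EUT dosing errors. No endpoint, analysis set or analysis is affected.

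The conclusion rests on a literal reading of Section 6.7 and on the protocol text at hand. The titration figure, the EUT Pharmacy Manual and any SRC working document are not available here. If one of them has the SRC assign EUT doses or defines an EUT overdose, the gap would close in practice, though Section 6.7 should still say so.

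**What to change.** Replace the first sentence of Section 6.7 with:

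> An overdose is any TPIP received in excess of the single dose assigned by the SRC (inpatient treatment period, Section 4.3.1) or in excess of the daily dose currently prescribed by the Investigator under Section 1.3.2.2 (EUT period, including any taper).

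Two additions may look attractive and should be left out. A separate limb for more than 640 µg in a day is redundant, since no prescribed EUT dose exceeds 640 µg. A sentence making EUT laboratory tests after an overdose conditional on Medical Monitor agreement would cut across the discretion that Section 8 gives the Investigator for safety samples. Section 6.7 already has the frequency and duration of plasma sampling settled with the study team and Medical Monitor.

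The cost is one sentence in the next amendment and a line in site training. The downside is some extra Medical Monitor contacts, and some expedited reports for mild symptoms after a home dosing error, such as the cough or headache that Section 1.3.2.2 lists as common with this drug class.
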